### *Per-protocol Set*

A supportive analysis may be performed by excluding subjects with important deviations from the protocol that may substantially affect the results of the primary efficacy analyses. The final determination on protocol violations, and thereby the composition of the Per-protocol Set, will be made prior to locking the clinical database and final analysis and will be documented in the statistical analysis plan (SAP).

### *PK-evaluable Set*

The PK-evaluable Set consists of treated subjects with adequate blood sampling to estimate at least 1 PK parameter.

## 8.3 Determination of Sample Size

### *Escalation Phase*

Up to 6 subjects may be enrolled in each dose cohort evaluated during the escalation phase. The minimum number of subjects enrolled in each cohort and the dose-step increments between adjacent cohorts will be based on a standard 3 + 3 dose escalation scheme ([Section 3.2](#)). A maximum of 36 subjects will be enrolled between up to 6 dose cohorts. The actual number enrolled is dependent upon the observed safety profile, which will determine the number of subjects per dose cohort, as well as the number of dose escalations required to achieve the MTD.

### *Expansion Phase*

For the purpose of broadly characterizing preliminary anti-tumor activity, a 95% one-sided confidence interval will be calculated according to [Table 8-1](#) for each cohort of 12 to 15 subjects evaluated. The original number of subjects was chosen largely based on clinical and feasibility considerations in light of the number of distinct cohorts to be evaluated. Although the number of subjects to be enrolled in an individual cohort is limited, the number of responses and any other indicators of clinical benefit that are observed within a cohort can be used to assess in a preliminary manner whether the true overall response rate is either unacceptably low or sufficiently high to warrant further evaluation in this or a future study. For example, if 12 subjects are enrolled within a cohort, the probability of observing no responses is low (i.e., < 1%) when the true overall response rate is 40% or higher. Similarly, the probability of observing 3 or more responses is high (i.e., 92%) when the true overall response rate is 40% or higher. When the true overall response rate is only 10%, the probability of observing 3 or more responses is 11%.

After a preliminary evaluation of both the tolerability of treatment and any early signs of clinical benefit as characterized by overall response rate, prolonged progression-free intervals, or clearance of minimal residual disease, a hematologic disease cohort may be expanded (and, if appropriate, further refined by disease characteristics) to a maximum of 40 subjects to further evaluate clinical benefit.

**Table 8-1: 95% Lower Confidence Limits for Response Rate**

Number of Subjects	Number of Responses					
	3	4	5	6	7	8
10	9%	15%	22%	30%	39%	49%
11	8%	14%	20%	27%	35%	44%
12	7%	12%	18%	25%	32%	39%
13	7%	11%	17%	22%	29%	35%
14	6%	10%	15%	21%	26%	33%
15	6%	10%	14%	19%	24%	30%

For the phase 1b portion (Part 2) of the study, the cohort size for selected cohorts has been increased to 40 subjects. This is to improve the precision of the overall response rate (ORR) estimate. For example, for an ORR of 30%, in 10 subjects, the lower confidence limit (LCL) of a 95% one-sided confidence interval is 8.7%, or a distance of 21.3% (30-8.7) from the ORR. When the sample size is increased to 40 for the same ORR, the LCL is 18.3%, or a distance of 11.7% (30-18.3) from the ORR. This anticipated improvement in the precision of the point estimate will be particularly important given the relative heterogeneity of the enrolled population.

#### *Expansion Phase Part 3: CTCL and PTCL Cohorts*

For the phase 1b (Part 3) expansion cohorts for CTCL and PTCL, the cohort size has been selected based upon a Simon optimal 2-stage design, with the low and high boundaries of the response rate being 10% (not effective) and 30% (warrants further study) respectively, and a power of 90% and an alpha of 0.05. The calculations were performed using PASS 14 (NCSS, 2015) and the Optimum design chosen. The total sample size is 35 subjects per cohort under the scenario described below. For the first stage, a total of 18 subjects will be enrolled in each cohort. At the end of Stage 1, if 2 or fewer responders are observed per cohort, enrollment in this cohort will be terminated, otherwise, enrollment will proceed to the second stage and an additional 17 subjects will be enrolled per cohort for a total of 35 subjects per cohort. At the end of the second stage, if 6 or fewer responders are observed per cohort, the drug will be rejected for further testing in this indication. The probability of early termination (PET) = 0.734 at the end of the first stage if the true response rate is less than 10%.

N1	R1	PET	N	R	Average N	Alpha	Beta
18	2	0.734	35	6	22.53	0.047	0.098

#### *Part 4 - Phase 1b Dose Optimization*

Up to 6 DLT evaluable subjects may be enrolled at each dose level evaluated during the escalation phase. The number of subjects enrolled at each dose level and the dose-step increments between adjacent dose levels will be based on a 3 + 3 dose escalation scheme (Section 3.2.2). Once the MTD or a recommended dose is estimated (with the required six DLT-evaluable patients at that dose level), an additional six patients will be treated at that dose level (for a total of twelve patients). These additional patients will allow further examination of the safety and tolerability of the dose and a preliminary examination of the efficacy of the dose. With twelve patients, if the observed response rate is 33%, the lower bound of a two-sided 90% confidence interval would be 0.12. The maximum width of the 90% CI would be 0.51.

We expect to accrue approximately 25 patients in Part 4. The actual number required will depend upon the observed safety profile, which will determine the number of subjects per dose level, as well as the number of dose escalations required to achieve the MTD or the recommended dose.

## **8.4 Statistical Methods**

The statistical analyses performed for this study will be presented by study phase. For the escalation phase, tabulations will be provided by dose cohort and overall. For the expansion phase, tabulations will be provided by disease cohort and overall. Some analyses may be performed based on the dose escalation and expansion phases combined.

The statistical analyses will be performed using SAS® version 9.2 or later (SAS Institute Inc, Cary NC). Programming specifications will be prepared which describe the datasets and variables created for this study. The datasets will be prepared using the most recent version of CDISC's Study Data Tabulation Model (SDTM) and Analysis Dataset Model (ADaM). The source SDTM and ADaM datasets from which a statistical analysis is performed (including interim safety reviews) will be archived with the Sponsor.

### **8.4.1 Subject Disposition**

The number of subjects included in the safety, PK, pharmacodynamic, and anti-tumor activity analyses will be summarized, along with the reason for exclusion from one or more analysis populations. Subjects discontinuing from study drug and the primary

reason for discontinuation will be summarized. Subjects withdrawing from study and the primary reason for withdrawal will be summarized in a similar manner.

#### **8.4.2 Demographics and Baseline Characteristics**

Descriptive summaries of demographic and baseline characteristics for all enrolled subjects will be tabulated by study phase – overall and by dose for Phase 1a (dose escalation/dose finding stage) and overall and by disease cohort for the additional subjects. Each cohort to be presented will be defined in the SAP to provide guidance for the tabulation summaries.

This format of presentation will be used for the safety, efficacy, PK, immune response and biomarker presentations.

#### **8.4.3 Extent of Exposure**

The overall duration of study drug administration in weeks will be tabulated for each subject and summarized by study phase. For each subject, the average dose (in mg) of TTI-621 administered and cumulative dose (in mg) administered will be calculated. These data will be further summarized for each cohort by calculating the mean, standard deviation, median, and range of these values. The number and proportion of subjects with one or more dose modifications (i.e., reduction or delay) will be tabulated along with the reason for modification.

#### **8.4.4 Safety Analyses**

The SRC, as outlined in [Section 3.4](#), will oversee all safety aspects of the study and make recommendations to the Sponsor.

Safety will be assessed by clinical review of all relevant parameters including AEs, serious adverse events (SAEs), laboratory values, vital signs, ADA, and ECG results. Unless specified otherwise, safety will be analyzed using the Safety Analysis Set defined in [Section 8.2](#). The results of these analyses will be presented by study phase. Some safety analyses, such as ADA, may be performed based on the dose escalation and expansion phases combined.

Summary tables and listings will be provided for all reported treatment-emergent AEs (TEAEs), defined as AEs that start on or after the first administration of study drug. The reported AE term will be assigned a standardized preferred term using the current version of the Medical Dictionary for Regulatory Activities (MedDRA).

TEAEs will be summarized based on the number and percentage of subjects experiencing the event by MedDRA System Organ Class and preferred term. As outlined in [Section 9.2](#), the causal relationship between the occurrence of an AE and study drug will be judged by the Investigator. In the event a subject experiences repeat episodes of the same AE, then the event with the highest severity grade and strongest causal relationship to study drug will be used for purposes of incidence tabulations. Tabular summaries will be provided for:

- all TEAEs
- TEAEs by study drug relationship (related, not related) and maximum severity grade
- TEAEs with action of study drug delayed/interrupted or treatment reduced
- TEAEs with action of study drug discontinued
- SAEs

For the escalation phase, the observed DLT rate in each cohort will be calculated by the crude proportion of subjects who experience DLT. Multiple concurrent AEs leading to DLT will be considered a single DLT. The estimate of the DLT rate will be accompanied by a 95% exact binomial confidence interval (CI).

All deaths that occur on study (defined as during treatment or within 30 days of treatment discontinuation) will be reported in a subject listing, which will include the primary cause of death and the number of days between the date of the last dose of study drug and death.

Hematology and serum chemistries will be summarized in a descriptive manner by calculating the mean, standard deviation, median, and range for baseline, minimum postbaseline value, maximum postbaseline value, average postbaseline value, and last postbaseline value. Laboratory values will be assigned toxicity grades when available using the NCI CTCAE scale and will be included as AEs if applicable. Directional shifts in laboratory toxicity grades (comparing baseline grade with worst postbaseline grade) will be analyzed using standard shift tables, presenting number and proportion of subjects and their maximum grade shift. Laboratory values taken during the PK sampling may be presented separately if appropriate; the final decision will be recorded in the SAP.

Vital signs will be summarized in a descriptive manner by calculating the mean, standard deviation, median, and range in the same manner described for laboratory

values. The results of the 12-lead ECG assessments will be summarized in the same manner as described for laboratories and vital signs.

The incidence, onset time, and titer of ADA will be summarized by descriptive statistics. The possible effects of ADA on PK (such as TTI-621 exposure as measured by  $C_{max}$  and AUC after seroconversion), efficacy, and safety of TTI-621 will be explored. Details will be provided in the SAP.

Prior and concomitant medications will be coded to the generic term using the current version of the World Health Organization Drug Dictionary and will be tabulated by cohort and listed by subject.

#### 8.4.5 PK Analyses

The PK of TTI-621 will be estimated from concentration-time data using noncompartmental methods. The reporting of PK parameters will be determined based on the final parameter analysis on the available data. Parameters to be assessed may include, as appropriate,  $AUC_{0-\tau}$ ,  $AUC_{0-\infty}$ ,  $T_{max}$ ,  $C_{max}$ ,  $t_{1/2}$ , clearance, and volume of distribution. CCI

All final PK analyses will be defined in the final PK analysis plan and/or final SAP as appropriate.

#### 8.4.6 Efficacy Analyses

Efficacy analyses will be conducted using the Full Analysis Set and, where appropriate, the Per-protocol Set; in addition, the overall response rate will also be presented for the Response-Evaluable Set.

The overall response rate will be estimated for each cohort using disease-specific response criteria (see [Section 7.14.1](#)). The duration of response (DOR) will be calculated for a subject who achieves a response, and is defined as the number of weeks from the start date of the response (and subsequently confirmed) to the first date recurrent or progressive disease is documented. If a subject dies, irrespective of cause, without documentation of recurrent or progressive disease beforehand, then the date of death will be used to denote the response end date.

Progression-free survival (PFS) is defined as the number of weeks from the date of the first dose of study drug to the earliest of documented recurrent or progressive disease or death due to any cause without prior progression. Leukemia-free survival (LFS) will be calculated in the same manner, as appropriate.

DOR and PFS will be summarized descriptively using the Kaplan-Meier method with 95% CI calculated using Greenwood's formula. Median follow-up for each endpoint will be estimated according to the Kaplan-Meier estimate of potential follow-up. The PFS rate at selected landmarks (e.g., 6 months) and corresponding 95% CIs will be estimated using the Kaplan-Meier method. Greenwood's formula will be used to calculate the standard errors of the Kaplan-Meier estimate and upper and lower limits of the 95% CI.

For DOR and PFS, subjects who meet one or more of the following conditions will be right-censored as follows:

- subjects with no baseline or postbaseline disease assessments unless death occurred prior to the first planned assessment (in which case the death will be considered a PFS event)
- subjects who initiate subsequent anticancer therapy in the absence of documented progression
- subjects who die or have disease progression after missing 2 or more consecutively scheduled disease assessment visits
- subjects who are last known to be alive and progression-free on or before the data cut-off date

For such subjects, the progression or censoring date will be determined based on described conventions (Food and Drug Administration, 2007), as outlined in the SAP.

#### **8.4.7 CTCL and PTCL Cohorts**

##### **Phase 1b Part 3: CTCL and PTCL Cohorts**

Radiographic disease assessments for CTCL and PTCL will be centrally reviewed. Each of the 2 cohorts (CTCL and PTCL) will be evaluated separately for the potential for further study using the Simon 2-stage design. For the first stage, a total of 18 response-evaluable subjects will be reviewed in each cohort; if 2 or fewer responders are observed per cohort, enrollment in that cohort will be terminated. Otherwise, enrollment will proceed to the second stage and an additional 17 response-evaluable subjects will be enrolled per cohort for a total of 35 response-evaluable subjects per cohort. At the end of the second stage, if 6 or fewer responders are observed per cohort, the drug will be rejected for further testing in this indication. If more than the required number of response-evaluable patients are available (i.e., >18 or >35), the first 18 or 35, respectively, would be used.

## Phase 1b Part 4: CTCL Cohorts

The subjects enrolled to phase 1b Part 4 will not require submission of scans for central review in real time, but might be requested by sponsor retrospectively.

CCI

## 9 ADVERSE EVENTS AND SAFETY REPORTING

An AE is any unfavorable medical occurrence in a subject administered investigational product, whether or not thought to have a causal relationship with the treatment. An AE can therefore be any unfavorable and unintended sign, symptom, or disease temporally associated with the use of the investigational product. For the purposes of this study, events which are unequivocally due to disease progression should not be reported as AEs. Symptoms of the disease under study/lack of efficacy should not be classified as AEs as long as they are within normal day-to-day fluctuations or expected progression of the disease.

The development of a new cancer should be regarded as an AE and will generally meet at least one of the serious AE criteria. New cancers are those that are not the primary reason for administration of study treatment and have been identified after the subject's inclusion in this study. They do not include metastases of the original cancer.

All AEs, complaints, or symptoms that occur from the start of the first dose of study treatment are to be recorded on the appropriate case report form (events ongoing prior to consent are considered medical history unless they worsen during study). Documentation must be supported by an entry in the subject's source medical records. Laboratory abnormalities requiring treatment or considered by the Investigator to be clinically relevant should be reported in the case report form as an AE. Each AE is to be evaluated for duration, severity, and causal relationship with the investigational product.

### 9.1 Grading and Severity of Adverse Events

The Investigator will grade the severity of each AE using, when applicable, the current version of the CTCAE. In the event of an AE for which no grading scale exists, the Investigator will classify the AE as mild, moderate, severe, life-threatening/debilitating, or fatal, as defined below.

- Mild – An event that is usually transient in nature and generally not interfering with normal activities
- Moderate – An event that is sufficiently discomforting to interfere with normal activities
- Severe – An event that is incapacitating with inability to work or do usual activity, or inability to work or perform normal daily activity
- Life-threatening/debilitating – An event that puts the subject at immediate or potential risk of death, requires hospitalization, or which drastically impacts a subject's well-being

- Fatal

## 9.2 Adverse Event Attribution

In early human trials, the relationship of an adverse event to the drug is not fully known. Therefore, all AEs should be considered relevant to determining DLT and to reporting unless the event can clearly be determined to be unrelated to the drug. The Investigator will determine whether each AE is considered related to investigational product or not using these categories:

- Related – the time course between administration of investigational product and the occurrence or worsening of the AE is consistent with a possible, likely, or definite causal relationship and no other cause (concomitant drugs or therapies, complications, the primary disease, comorbidities, etc.) can be confirmed
- Unrelated – the time course between the administration of investigational product and the occurrence or worsening of the AE rules out a causal relationship and another cause (concomitant drugs or therapies, complications, the primary disease, comorbidities, etc.) is confirmed

The following factors should also be considered in the determination of attribution: preclinical pharmacology, PK, and toxicology of the investigational product, whether a particular response is a class effect, concomitant medications, and the primary disease as well as underlying intercurrent conditions.

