## 1.7 Anticipated or Possible Risks in Human Subjects

### *Summary of Dose-Escalation Safety Data*

Data from the first 18 subjects enrolled in the dose-escalation phase of the study show that TTI-621 has been reasonably well tolerated. Transient, dose-dependent decreases in platelets without clinical sequelae occurred in the hours following infusion in the majority of subjects exposed to TTI-621. Thrombocytopenia was relatively brief with recovery to baseline platelet counts by the next weekly dose and appeared attenuated with weekly TTI-621 exposure. Other Grade 3/4 cytopenias (monocytes, neutrophils, and lymphocytes) were also frequently observed; all were transient and resolved without sequelae.

The majority of subjects experienced mild to moderate infusion-related reactions (IRRs) that typically occurred after the first TTI-621 infusion only. IRRs were reported across all dose cohorts with no obvious dose relationship and occurred despite premedication with an antihistamine and acetaminophen.

Three subjects experienced reversible Grade 3 hypophosphatemia in the days following their first infusion of TTI-621. Hypophosphatemia in 1 of the 3 subjects was considered related to TTI-621 and was therefore reported as a DLT. The event rapidly resolved without intervention. Hypophosphatemia was considered unrelated to TTI-621 in the other 2 subjects and their phosphate levels were corrected by oral phosphate.

No subjects in either the 0.05 mg/kg/week or 0.1 mg/kg/week dose groups experienced dose-limiting toxicity (DLT). However DLTs were reported for 2 of 5 subjects treated at the 0.3 mg/kg/week dose: 1 subject with Grade 4 thrombocytopenia and 1 subject with Grade 4 thrombocytopenia and Grade 3 elevated alanine aminotransferase/aspartate aminotransferase (ALT/AST). Upon review of cumulative adverse events (AEs) and laboratory values, the Safety Review Committee (SRC) recommended proceeding with

enrollment at an intermediate dose level of 0.2 mg/kg TTI-621 (Cohort 2a), and to dose reduce all subjects participating in the 0.3 mg/kg cohort to the 0.2 mg/kg dose level (one subject was dose reduced to the 0.1 mg/kg dose level).

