Seven subjects were subsequently enrolled in Cohort 2a, 6 of whom were DLT evaluable. One of the 6 DLT-evaluable subjects experienced a DLT of Grade 3 hypophosphatemia; therefore, the SRC declared 0.2 mg/kg as the MTD and enrollment to the expansion phase is currently underway. Similarly, a dose of 0.2 mg/kg/week in combination with rituximab was initially recommended for subjects enrolled in the combination treatment arm; however 1 subject treated with TTI-621 experienced an SAE of Grade 3 gastrointestinal bleed; therefore, current subjects receive an initial dose of 0.1 mg/kg TTI-621 administered together with the combination partner agent.

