### **3.3.3 Definition of Dose-limiting Criteria for Phase 1b Part 4 (Amendment 9)**

Dose-limiting toxicity is defined as any of the following TAEs that occur during the 21-day DLT treatment/observation period (including the pre-dose tests on Day 22/Week 4 Day 1) and that are considered at least possibly related to study treatment by the investigator. Note that any AEs for which the relationship to study treatment cannot be ruled out should be considered possibly related:

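### The Related and Unrelated definitions in Protocol Section 9.2 are not exhaustive and do not line up with the Part 4 DLT default, so the same event could be classified differently across sites

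*Protocol*

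**What the plan says.** Protocol Section 9.2 gives the investigator two categories.

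- Related: timing fits a causal link that is at least possible, and in addition "no other cause (concomitant drugs or therapies, complications, the primary disease, comorbidities, etc.) can be confirmed". Both conditions are required.
- Unrelated: timing "rules out a causal relationship and another cause (concomitant drugs or therapies, complications, the primary disease, comorbidities, etc.) is confirmed". Again both conditions are required.

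The same section opens with a conservative default: "all AEs should be considered relevant to determining DLT and to reporting unless the event can clearly be determined to be unrelated to the drug".

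In Part 4, the DLT definition requires that the investigator consider the event at least possibly related, and adds that "any AEs for which the relationship to study treatment cannot be ruled out should be considered possibly related". This appears in Protocol Section 3.3.3, in the Synopsis and in SAP Section 1.1.3.

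SAP Section 3.5.1 lists the CRF items for each event. Relationship to TTI-621 has two values, related or unrelated. Whether the event was a DLT is a separate item.

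**The concern.** Each category joins its two conditions with *and*, so the categories are not complements of each other. An investigator whose patient has an event with consistent timing, and also another confirmed cause, finds that neither definition is met but must still tick one of two boxes. One site may tick unrelated because Related fails. Another may tick related because Unrelated fails. Both can point to the text.

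The entry is used in several places:

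- The related-TEAE summaries in SAP Section 3.5.1: any grade, Grade 3 or higher, serious, leading to withdrawal, and leading to death.
- Protocol Table 6-1, which has separate rows for Grade 3 or greater non-hematologic toxicity that is related and not related to TTI-621.
- Protocol Section 6.5.4, where Part 3 dose intensification depends on the grade of treatment-related events.
- Protocol Section 9.4, where, after 30 days from the last dose, reporting is restricted to treatment-related events and events of special interest.

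If sites resolve the gap differently, the related-event rates mix drug effect with site convention, and these rules are applied unevenly.

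**Working it through.** **Step 1. Enumerate the cases.** Section 9.2 uses two yes/no attributes: whether timing is consistent with causality or rules it out, and whether another cause is confirmed. The Part 4 DLT default is set beside the result.

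| Timing | Other cause | Meets Related? | Meets Unrelated? | Section 9.2 category | Part 4 DLT default |
|---|---|---|---|---|---|
| Consistent | Not confirmed | Yes | No | Related | Possibly related |
| Consistent | Confirmed | No | No | None | Possibly related, unless the relationship is ruled out |
| Rules out | Not confirmed | No | No | None | Not related |
| Rules out | Confirmed | No | Yes | Unrelated | Not related |

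Two of the four combinations have no category. The CRF has no third value, and no passage in the two documents says which box to use.

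**Step 2. Compare with the defaults.** In row 2, both the opening of Section 9.2 and Section 3.3.3 lean toward counting the event, but the Related definition does not admit it. Section 9.2 does not call it Unrelated either, because its timing does not rule out causality. This is a gap and a misalignment. In row 3 the DLT default already gives the answer, so the gap there concerns only the CRF entry.

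**Step 3. What stays open for DLTs.** The text does not say whether a confirmed alternative cause is enough by itself to rule out the drug, or whether the CRF relatedness entry is meant to determine the DLT call.

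**Step 4. A what-if for DLT counts.** Section 9.2 states no figure. The related figure is the SAP Section 1.2.2 table of escalation probabilities for the 3+3 design. With true DLT rate p and q = 1 − p,

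P(escalate) = q³ + 3pq² × q³.

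For p = 10% to 80% this gives 0.906, 0.709, 0.494, 0.309, 0.172, 0.082, 0.032 and 0.009, matching the SAP's 0.91, 0.71, 0.49, 0.31, 0.17, 0.08, 0.03 and 0.01.

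Suppose a share f of DLT-type events fell in row 2 and were not counted, so that p becomes p(1 − f). The documents do not give f, so it is an assumption and is varied.

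| True DLT rate | f = 0 | f = 10% | f = 20% | f = 1/3 | f = 50% |
|---|---|---|---|---|---|
| 30% | 0.494 | 0.557 | 0.622 | 0.709 | 0.814 |
| 40% | 0.309 | 0.378 | 0.454 | 0.564 | 0.709 |

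For example, at p = 30% and f = 20%, the counted rate is 0.30 × 0.80 = 0.24, and 0.76³ + 3(0.24)(0.76²)(0.76³) = 0.439 + 0.183 = 0.622. These figures apply only if sites set aside the written default and leave such events out of the DLT count. They do not estimate the size of this point.

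**The case against.** The strongest reply is that the DLT count is already protected. The opening of Section 9.2, Section 3.3.3, the Synopsis and SAP Section 1.1.3 all default toward counting. The DLT flag is separate from the relatedness box. Under Protocol Section 3.4 the Safety Review Committee reviews each Part 4 cohort's safety data and decides on escalation. This stands and limits the point, although no passage says that the committee re-adjudicates the investigator's attribution.

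Other limits also stand:

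- The primary endpoint is incidence and severity of all AEs, and the all-TEAE tables do not depend on relatedness.
- The platelet and neutrophil retreatment thresholds in Section 6.5.2 apply before each dose without an attribution test.
- The general dose-hold text in Section 6.5.1 covers events that are only possibly related, and Section 6.5.1 also allows withholding for unrelated events.
- Some competing causes are handled elsewhere: Grade 4 anemia is a DLT only if underlying disease does not explain it, and Section 9 excludes events unequivocally due to progression from AE reporting.
- The CRF completion instructions and Study Manual are not among the documents and may say more.

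A reader might infer that Section 9.2 contradicts the DLT rule, or that each site decides the DLT count for itself. The documents support neither: the ambiguous event is left without a category, not called Unrelated, and a default exists.

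A reader might also take the Part 1 experience as proof. Section 1.7 reports that "Hypophosphatemia in 1 of the 3 subjects was considered related to TTI-621 and was therefore reported as a DLT" and that, at 0.2 mg/kg, "One of the 6 DLT-evaluable subjects experienced a DLT of Grade 3 hypophosphatemia". It does not say that the two events called unrelated had another confirmed cause, or in which cohort they occurred. Part 1 also predates the Section 3.3.3 definition. Likewise, the 49 of 179 subjects with Grade 4 platelet decreases span all cohorts and do not count attribution decisions. Neither figure measures this gap.

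**Conclusion.** The point holds as a drafting defect with a limited but real effect. Two of the four timing-by-cause combinations have no category, although a binary entry is required. The Related definition is narrower than the defaults in Section 9.2's own opening and in the Part 4 DLT definition.

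The main exposure is the related-TEAE tables and the rules conditioned on relatedness in Table 6-1, Section 6.5.4 and Section 9.4. In Section 9.4 it is smaller, because events of special interest are reported after 30 days whatever their attribution. No DLT, MTD or dose decision is shown to have turned on the gap.

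The number of affected events cannot be derived from the documents. The conclusion rests on reading the two conditions in each definition as jointly required, which is what the text says, and on no unseen instruction resolving the entry. It is worth correcting because the change is small and the related-event tables are a main safety output.

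**What to change.** Reconcile Section 9.2 with Section 3.3.3 by making the categories complementary:

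- Unrelated: a causal relationship to TTI-621 is ruled out.
- Related: every other event, including when another possible cause is present.

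Carry the same wording into the CRF completion guide, so that the relatedness entry and the DLT assessment start from one definition.

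The cost is protocol and CRF-guide wording. The downside is that somewhat more events will be called related, which is consistent with the conservative opening of Section 9.2. Because Table 6-1 and Section 6.5.4 depend on relatedness, the clinical team should check that those rules still read as intended under the revised definition. No change to them is proposed here.
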